### 5.2.3 Dose Modification for Apalutamide

Apalutamide dose reductions due to toxicities other than rash are described in the table immediately below. Management of rash, including dose reductions, is described in Section 5.4. Apalutamide dose may be reduced as follows: first dose-level reduction to 180 mg/day, second dose-level reduction to 120 mg/day. If further dose reduction is required, apalutamide should be discontinued.

Event	Clinically Significant Hematologic and Non-Hematologic AEs Deemed Related to Apalutamide
Grade 1 or 2	Dose delay up to 4 weeks or dose reduction at the discretion of the investigator.
Grade 3	Hold apalutamide until AE has improved to Grade $\leq 1$ or baseline and resume with a dose reduction. If apalutamide cannot be restarted within 4 weeks, it should be discontinued. Discontinue for Grade 3 toxicity that recurs after 2 dose reductions.
Grade 4	Permanently discontinue apalutamide.

Doses re-escalation back to the previous dose level may be permitted upon discretion of the Principal Investigator.

### 5.3 Management of Infusion-related Reactions

Guidelines for the management of IRRs are described in Table below. A reaction may manifest with fever, chills, rigors, headache, rash, pruritus, arthralgias, hypo- or hypertension, bronchospasm, or other symptoms. IRRs should be graded per NCI-CTCAE criteria.

	Management of Infusion Related Reactions
Grade 1	No intervention indicated; remain at bedside and monitor subject until recovery from symptoms. Consider diphenhydramine 50 mg (or equivalent) or paracetamol 325 to 1000 mg (acetaminophen) or both at least 30 minutes before additional study drug administration.
Grade 2	Stop infusion; start IV saline infusion; give diphenhydramine 50 mg (or equivalent) IV or paracetamol 325 to 1000 mg (acetaminophen) or both; consider corticosteroids and bronchodilator therapy. Restart infusion at 50% of initial rate: if no further complications ensue after 30 minutes, the rate may be increased to 100% of the original infusion rate; monitor subject closely. Symptoms recur: discontinue treatment at that visit; administer diphenhydramine 50 mg IV.

Grade 3-4	
Stop infusion; start IV saline infusion, bronchodilators, epinephrine 0.2 to 1 mg of a 1:1,000 solution for subcutaneous administration or 0.1 to 0.25 mg of a 1:10,000 solution injected slowly for IV administration, or diphenhydramine 50 mg IV with methylprednisolone 100 mg IV (or equivalent), or all 4, as needed.
 
Subject should be monitored until the investigator is comfortable that the symptoms will not recur. Study drug will be permanently discontinued. Investigators should follow their institutional guidelines for the treatment of anaphylaxis.
 
In the case of late-occurring hypersensitivity symptoms (e.g., appearance of a localized or generalized pruritus within 1 week after treatment), symptomatic treatment may be given (e.g., oral antihistamine, or corticosteroids).

Secondary Prophylaxis	
Prophylactic medications (after initial event): diphenhydramine 50 mg (or equivalent) or paracetamol 325 to 1000 mg (acetaminophen) or both at least 30 minutes before additional study drug administrations; if necessary, corticosteroids (recommended dose: up to 80 mg of IV methylprednisolone or equivalent) may be used.

## 5.4 Management of Rash

Interventions for the management of skin rash are listed in Table below. Document skin rash of any type or grade by de-identified photographs.

For skin rash with any component of desquamation, mucosal involvement, or pustules:

- Stop dosing with apalutamide and cetrelimab
- Refer to dermatologist for evaluation
- Consider skin biopsy in patients experiencing Grade  $\geq 2$  rash, if clinically indicated per conventional (standard of care) management.

*OPTIONAL: In the event that one or more standard of care skin biopsies are conducted, extra tissue may be collected for research (immune correlate assay to explore the mechanism of skin rash) only for patients who give optional consent for the extra tissue collection. Refer to the Lab Manual and Section 6.4.5 for additional information.*

Management of Drug Related Rash	
Grade 1	
 
• Reduce apalutamide dose by one dose level
 
• Continue cetrelimab at current dose
 
• Initiate oral corticosteroids. Taper corticosteroid doses as clinically indicated while monitoring clinically for worsening symptoms
 
• Consider topical steroid cream
 
• Reinitiate oral H1 receptor blockers, if previously discontinued
 
• Consider re-starting H2 receptor blockers and/or montelukast, if previously discontinued
 
• Monitor for change in severity
 

Grade 2 (or symptomatic grade 1 a )	
 
• At principal investigator discretion, hold cetrelimab and apalutamide for up to 28 days and reinitiate when rash Grade is ≤1
 
• Reduce apalutamide dose by one dose level
 
• Initiate oral corticosteroids or consider escalating corticosteroid dose if already prescribed. Taper corticosteroid doses as clinically indicated while monitoring clinically for worsening symptoms
 
• Consider topical steroid cream
 
• Reinitiate oral H1 receptor blockers, if previously discontinued
 
• Consider re-starting H2 receptor blockers and/or montelukast, if previously discontinued
 
• Monitor for change in severity
 

Grade ≥ 3 b	
 
• Hold cetrelimab and apalutamide for up to 28 days and reinitiate when rash
 
• Grade is ≤1; if after 28 days, the rash has not resolved to Grade ≤1, contact the sponsor to discuss further management and possible discontinuation of study drug
 
• Reduce apalutamide dose by one dose level at time of re-initiation
 
• Initiate oral corticosteroids or consider escalating corticosteroid dose if already prescribed. Taper corticosteroid doses as clinically indicated while monitoring clinically for worsening symptoms
 
• Consider topical steroid cream
 
• Initiate oral H1 and H2 receptor blockers and montelukast, if previously discontinued
 
• Monitor for change in severity
 
• Consider early referral to dermatologist
 

a. Patient presents with other rash-related symptoms such as pruritus, stinging, or burning

b. If there is blistering or mucosal involvement, stop cetrelimab and apalutamide dosing immediately.

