### 5.2.1 Retreatment Criteria for Cetrelimab and Apalutamide

**Table 5.2 Retreatment Criteria**

Adverse Event	Requirements before each study agent administration
Absolute neutrophil count	$\geq 1.0 \times 10^9/L$
Platelet count	$\geq 50 \times 10^9/L$ with or without platelet transfusions and/or growth factors
Hemoglobin	$\geq 8.0 \text{ g/dL}$ with or without transfusion, growth factors, or both
Fasting glucose, if prompted by HbA1c	$\leq 250 \text{ mg/dL}$
Hyperthyroidism	Grade $\leq 2$
AST and ALT	$\leq 3 \times \text{ULN}$ ( $\leq 5 \times \text{ULN}$ for patients with liver metastases)
Total bilirubin	$\leq 1.5 \times \text{ULN}$
Rash	Grade $\leq 2$
Other clinically significant toxicity 	Recovery to Grade $\leq 1$ or baseline

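### Section 5.4's any-grade stop-and-refer rule for rash omits blistering, so read literally a Grade 1-2 blistering rash has no blistering-specific required stop, and blistering alone requires no dermatology referral at any grade

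*Combined protocol and SAP*

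**What the plan says.** Section 5.4 (Management of Rash) has two layers.

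The first is a short list of features that call for action whatever the grade: "For skin rash with any component of desquamation, mucosal involvement, or pustules". For these, dosing of both drugs stops and the patient is referred to a dermatologist. Neither action is optional.

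The second is a table by grade:

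- **Grade 1:** apalutamide goes down by one level, the instruction for the antibody is "Continue cetrelimab at current dose", and a course of oral steroids is begun and later tapered on clinical grounds.
- **Grade 2, or Grade 1 with symptoms such as pruritus, stinging or burning:** "At principal investigator discretion, hold cetrelimab and apalutamide for up to 28 days", with the same one-level apalutamide reduction and with corticosteroids started or an escalation considered.
- **Grade 3 or higher:** both drugs are held for up to 28 days, and early dermatology referral is to be considered. This row alone carries footnote b: "If there is blistering or mucosal involvement, stop cetrelimab and apalutamide dosing immediately".

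All rows ask for monitoring for a change in severity. For every rash the section also says: "Document skin rash of any type or grade by de-identified photographs".

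**The concern.** The protocol gives two lists of warning signs in one section, and they do not match. Mucosal involvement is on both, so it is covered at every grade. Blistering is only in the footnote, and the footnote is attached to the one row that already requires both drugs to be held. The blistering trigger therefore sits where an interruption is mandatory anyway and is absent from the rows where none is.

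This bears on patient safety. Rash is a leading known toxicity of this combination. Section 1.6 reports Grade 3 or higher rash in 37.0% of 27 subjects in the Phase 1b study, and three of the six discontinuations for adverse events there were for rash. Section 5.4 is therefore likely to be used, and a sign that the protocol itself treats as grounds for an immediate stop should not depend on which row a clinician is reading.

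**Working it through.** The documents give no figure to reproduce and no arithmetic applies. The check is to follow a rash with blistering, and no desquamation, mucosal involvement or pustules, through every rule that could apply.

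**Within Section 5.4**

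| Rash | Stop or hold of both drugs | Dermatology referral |
|---|---|---|
| Blistering only, asymptomatic Grade 1 | None required; cetrelimab continues, apalutamide reduced one level | Not mentioned |
| Blistering only, symptomatic Grade 1 | Hold at the principal investigator's discretion | Not mentioned |
| Blistering only, Grade 2 | Hold at the principal investigator's discretion | To be considered |
| Blistering only, Grade 3 or higher | Immediate stop (footnote b) | To be considered |
| Mucosal involvement, any grade (for comparison) | Required stop | Required |

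The Grade 2 referral entry comes from Study Calendar footnote 9 and Sections 6.3.2.4 and 6.4.5. These ask only that referral for a biopsy be considered for Grade 2 or higher rash, if clinically indicated.

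**Other sections that might close the gap**

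1. *Table 5.2* sets the "Requirements before each study agent administration". Its rash row allows dosing at Grade 2 or lower. Its last row, for other clinically significant toxicity, needs recovery to Grade 1 or baseline. That row could block dosing at Grade 2 if blistering were recorded as an event separate from the rash, but rash has its own row and Grade 1 would pass in any case.
2. *Section 5.2.2* names Grade 3 rash as a reason to delay cetrelimab. Its general Grade 2 clause depends on the toxicity being intolerable or lasting more than 28 days. Neither depends on blistering, and both concern cetrelimab only.
3. *Section 5.2.3* sends rash back to Section 5.4. Its dose ladder runs 240, 180, 120 mg/day and then discontinuation, so a patient already at 120 mg/day who needs a further reduction would stop apalutamide. The dose level triggers that stop, not the blistering.
4. *Section 3.5*, and the best-interest clause in Section 5.2.2, let the investigator end treatment. They leave the decision to judgment and name no sign that triggers it.

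No rule outside footnote b makes blistering as such a reason to stop, and none makes dermatology referral mandatory for it.

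**The case against.** The strongest reply is that footnote b's own words contain no grade limit. Its other trigger, mucosal involvement, already applies at every grade through the opening rule, so the footnote was hardly meant as a rule for Grade 3 and above only. A clinician reading the single rash table could well stop both drugs for any blistering. That stands as a plausible reading and makes this a conflict between two pieces of text more than a plainly unsafe order. It does not remove the conflict, because the marker is on one row only and the Grade 1 row says in terms that cetrelimab continues. It also does nothing for referral, which the footnote does not mention.

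Second, the scenario is not shown to occur. The protocol grades by CTCAE version 5.0 but does not reproduce its rash or blistering criteria, so the documents cannot show how often a blistering rash would be graded 1 or 2, or coded as something else. The one rash rate given for the combination is for Grade 3 or higher, where footnote b applies without dispute. This stands, and it is why no frequency is offered.

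Third, safeguards exist: dose reduction, corticosteroids, monitoring, photographs, and the investigator's freedom to stop. They lessen the practical effect without supplying a required stop.

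A reader might go further and infer that a low-grade blistering rash can never lead to a required stop, or that the protocol orders dosing to continue through it. The documents do not support either. Stops can be required for other reasons, such as apalutamide already at its lowest level or intolerable or persistent Grade 2 cetrelimab toxicity. At Grade 2 and symptomatic Grade 1 a hold is expressly available. Only the asymptomatic Grade 1 row tells the site to continue cetrelimab.

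**Conclusion.** The point holds in a narrow form. Blistering is missing from the any-grade rule, although the same section treats it as grounds for an immediate stop. Read literally, a Grade 1 or 2 rash whose only special feature is blistering has no blistering-specific required stop, and blistering alone has no required dermatology referral at any grade.

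This rests on two assumptions: that footnote b binds only the row on which it is marked, and that blistering is graded as part of the rash and not as a separate event. The number of patients affected cannot be stated, since the documents give neither a Grade 1-2 rash rate for the combination nor the share that blister. The primary endpoint, sample size and analysis are unaffected. The change is worth making because it is a safety inconsistency that costs almost nothing to remove.

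**What to change.** In the opening rule of Section 5.4, add *of any grade* after the reference to skin rash and add *blistering* to the listed features, between desquamation and mucosal involvement. State that this rule takes precedence over the graded rows, and so over the rash row of Table 5.2. Footnote b can then simply refer back to the opening rule; repeating the full list there is unnecessary.

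The cost is a few words in one section and, in practice, a few more dose stops and dermatology referrals for low-grade blistering rash.

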## 6 Study Procedures and Schedule of Events

The study-specific procedures and assessments are detailed in this section and outlined in the Study Calendar – Section 6.1.

Screening assessments must be performed within 28 days prior to the first dose of investigational product, unless otherwise noted. Any results falling outside of the reference ranges may be repeated at the discretion of the investigator.

All on-study visit procedures are allowed a window of  $\pm$  3 days unless otherwise noted. Treatment or visit delays for public holidays or weather conditions do not constitute a protocol violation.

## 6.1 Study Calendar

Period/ Procedure	Screening	Cycle 1		Cycle 2+	End of Treatment	Safety Follow- up	Safety Follow-up	Long Term Follow-up
Study Day/Visit Day	Day -28 to -1 unless otherwise noted	D1 (± 3d)	D15 (± 3d)	D1 (± 3 days)		30 days (± 7 days) post-last dose	100 days (± 14 days) post-last dose	Every 90 days  (± 30 days)
Study Treatment/Drug Administration								
Apalutamide			X					
Cetrelimab infusion		X		X				
Administrative Procedures								
Informed Consent	X							
Clinical Assessments								
Medical History	X							
Concurrent Medications	X	X	X	X				
Physical Exam 	X 	X 	X 	X 	X 			
Vital Signs (blood pressure and heart rate)	X	X	X	X	X			
AE assessment	X	X	X	X	X	X	X 	
ECOG/Karnofsky Performance Status	X	X	X	X	X			
Survival/Long-term Follow-up 								X
Laboratory Assessments								
Hematology 	X	X	X	X	X	X		
Chemistry 	X	X	X	X	X	X		
Thyroid Function Tests 	X	X		X	X			
Serum PSA	X	X		X	X			
Serum Total Testosterone	X							
Whole blood peripheral immune markers 		X		X 	X			

Period/ Procedure	Screening	Cycle 1		Cycle 2+	End of Treatment	Safety Follow- up	Safety Follow-up	Long Term Follow-Up
Study Day/Visit Day	Day -28 to -1 unless otherwise noted	D1 (± 3d)	D15 (± 3d)	D1 (± 3 days)		30 days (± 7 days) post-last dose	100 days (± 14 days) post-last dose	Every 90 days (± 30 days)
Isolation of peripheral blood mononuclear cells (PBMC)				X 	X 			
Circulating tumor cells 		X 		X 	X 			
Circulating tumor DNA 		X 		X 	X 			
Imaging Procedures								
CT Chest, Abdomen, and Pelvis 	X			X				
Bone scan 	X			X				
CT/MR brain 								
Tissue Collection/ Biopsy								
Tumor Tissue Collection 	X				X			
Skin biopsy for Grade ≥2 rash, if clinically indicated 					X 			

 Patients will be followed for overall survival every 90 days (+/- 30 days) from last dose of study treatment. Follow up will be conducted via chart review and/or telephone call.

 Including complete blood cell (CBC) with differential and platelet count. All laboratory assessments have a window of +/- 3 days.

 Chemistry panel includes: sodium, potassium, chloride, bicarbonate, blood urea nitrogen (BUN)/creatinine, calcium, alkaline phosphatase (ALP), ALT/AST, total bilirubin. All laboratory assessments have a window of +/- 3 days.

 Thyroid function tests - including thyroid-stimulating hormone (TSH), with reflex free T4, total/free T3. Thyroid function tests will be performed on Day 1 of each Treatment Cycle.

 Whole Blood for peripheral immune marker assessment will be collected on C1D1 (pre-dose), C2D1 (pre-dose), C3D1 (pre-dose), and End of Treatment.

 Tumor assessment will be performed with CT Chest/Abdomen/Pelvis and whole-body bone scan during screening, C4D1 (-14d), C7D1 (-14d) and on D1 (-14d) of every 4 cycles thereafter (e.g. C11D1, C15D1). If PD by RECIST1.1/PCWG3, confirmatory scans are required ≥ 4 weeks following first scan showing progression. Lesions on chest x-ray are acceptable as measurable lesions when they are clearly defined and surrounded by aerated lung. However, CT is preferable.

 CT with contrast or MR brain is required during Screening only if history of brain metastases or clinical suspicion.

 Optional Tumor biopsy will be performed during Screening. Biopsy only required if no biopsy has previously been done. If no metastatic lesion is safely accessible to tumor biopsy, this requirement will be waived. Bone or soft tissue lesion is allowed, but soft tissue will be prioritized. If a patient has archival tissue obtained within 90 days of C1D1, and no intervening therapy between tissue acquisition and C1D1, the requirement for fresh tumor biopsy will be waived. Tumor biopsy at progression is

optional and should be the same lesion as Screening biopsy whenever feasible. Biopsy at PD also optional. Refer to Lab Manual for detail regarding tissue collection/biopsy.

 If a subject experiences a treatment-emergent rash of Grade  $\geq 2$ , consider referral to Dermatology for skin biopsy if clinically indicated per conventional (standard of care) rash management. See Section 5.4 for rash management.

OPTIONAL: In the event that one or more standard of care skin biopsies are conducted, extra tissue may be collected for research (immune correlate assay to explore the mechanism of skin rash) only for patients who give optional consent for the extra tissue collection. Refer to the Lab Manual and Section 6.4.5 for additional information.

 PBMCs will be isolated from blood of patients experiencing Grade  $\geq 2$  rash (within 14 days of symptom onset when feasible) and from patients which have not experienced any Grade rash at end of treatment.

 Whole blood will be collected on C1D1 (pre-dose), C2D1 (pre-dose), C3D1 (pre-dose), and End of Treatment. Samples were stored at Epic Sciences for circulating tumor cell analysis, however, as of Amendment 1.8 dated 07-24-2023, Epic Sciences is no longer analyzing these samples. All remaining samples stored at Epic Sciences will be returned to UCSF and stored at the UCSF CTSI lab. Whole blood will continue to be collected and stored at the CTSI for future research..

 Plasma for circulating tumor DNA analysis including 5-hydroxymethyl cytosine (5-hmC) sequencing will be collected on C1D1 (pre-dose), C2D1 (pre-dose), C3D1 (pre-dose), and End of Treatment. Plasma will be sent to the [name] laboratory at UCSF.

 Height at screening only. Weight at each physical exam visit (patient will self-report if PE is during a telemedicine visit).

 On Cycle 1 Day 15 and the End of Treatment (EOT) visit, the physical exam may be done via a telemedicine visit. Other physical exams must be performed in-person. Vital signs (BP and heart rate) will be self-reported by the patient when the physical exam is a telemedicine visit.

 If AE assessment done at EOT visit, just needs to be done at 30-day Safety Follow-Up

## 6.2 Participant Registration

A written, signed, informed consent form (ICF) and a Health Insurance Portability and Accountability Act (HIPAA) authorization must be obtained before any study-specific assessments are initiated. A copy of the signed ICF will be given to the subject and a copy will be filed in the medical record. The original will be kept on file with the study records.

All participants consented to the study will be registered in OnCore®, the UCSF Helen Diller Family Comprehensive Cancer Center Clinical Trial Management System (CTMS). The system is password protected and meets HIPAA requirements.

## 6.3 Schedule of Procedures and Observations

### 6.3.1 Pretreatment Period

#### 6.3.1.1 Screening Assessments

The Screening procedures and assessments must be completed within 28 days of initiating study treatment.

- Clinical Assessments
  - Complete medical history
  - Concomitant medication review
  - Physical examination (including height and weight) and vital signs (BP and heart rate)
  - AE assessment
  - Performance status
- Laboratory Assessments
  - Hematology labs - CBC with differential and platelet count
  - Blood chemistry assessment, including: ALP, ALT/AST, total bilirubin, calcium, BUN, creatinine, potassium, sodium, chloride, bicarbonate
  - Thyroid function tests - including thyroid-stimulating hormone (TSH), with reflex free T4 and total/free T3
  - Serum Prostate Serum Antigen (PSA)
  - Testosterone level
- Imaging Procedures
  - CT of Chest, Abdomen and Pelvis (with IV contrast unless contra-indicated)
  - Bone scan
  - CT or MR brain with contrast (only if history of brain metastases or clinical suspicion)
- Tumor Tissue Collection (optional): A pre-treatment core biopsy is only required of patients who have not had a previous biopsy. In these cases, a biopsy must be obtained prior to study enrollment for all patients with safely accessible lesion, unless metastatic biopsy has been previously obtained within 90 days of C1D1 without intervening systemic therapy. For all other patients, the biopsy is optional.

### 6.3.2 Treatment Period

#### 6.3.2.1 Study Procedures, Cycle 1, Day 1

- Study Treatment/Drug Administration
  - Initiation or continuation of apalutamide
  - Cetrelimab infusion
- Clinical Assessments
  - Concomitant medication review
  - Physical examination (including weight) and vital signs
  - AE assessment
  - Performance status
- Laboratory Assessments
  - Hematology labs - CBC with differential and platelet count
  - Blood chemistry assessment, including: ALP, ALT/AST, total bilirubin, calcium, BUN, creatinine, potassium, sodium, chloride, bicarbonate,
  - Thyroid function tests - including thyroid-stimulating hormone (TSH), free T4, total/free T3
  - Serum PSA
  - Whole blood peripheral immune markers (pre-dose)
  - Circulating tumor cells (pre-dose)
  - Circulating tumor DNA (pre-dose)

#### 6.3.2.2 Study Procedures, Cycle 1, Day 15

- Study Treatment/Drug Administration
  - Continuation of apalutamide
- Clinical Assessments
  - Concomitant medication review
  - Physical examination (including weight), may be done via a telemedicine visit
  - Vital signs (BP and heart rate)
  - AE assessment
  - Performance status
- Laboratory Assessments
  - Hematology labs - CBC with differential and platelet count
  - Blood chemistry assessment, including: ALP, ALT/AST, total bilirubin, calcium, BUN, creatinine, potassium, sodium, chloride, bicarbonate

#### 6.3.2.3 Study Procedures Cycle 2+, Day 1

- Study Treatment/Drug Administration
  - Continuation of apalutamide
  - Cetrelimab infusion

- Clinical Assessments
  - Concomitant medication review
  - Physical examination (including weight)
  - Vital signs (BP and heart rate)
  - AE assessment
  - Performance status
- Laboratory Assessments
  - Hematology labs - CBC with differential and platelet count
  - Blood chemistry assessment, including: ALP, ALT/AST, total bilirubin, calcium, BUN, creatinine, potassium, sodium, chloride, bicarbonate
  - Thyroid function tests - including thyroid-stimulating hormone (TSH), reflex free T4, reflex total/free T3 (D1 of every cycle)
  - Serum PSA
  - Whole blood peripheral immune markers (C2D1, C3D1, pre-dose)
  - Isolation of peripheral blood mononuclear cells (PBMC)
  - Circulating tumor cells (C2D1, C3D1, pre-dose)
  - Circulating tumor DNA (C2D1, C3D1, pre-dose)
- Imaging Procedures
  - CT of Chest, Abdomen and Pelvis (with IV contrast unless contra-indicated) and whole-body bone scan (C4D1, C7D1, and D1 of every 4 cycles thereafter). Scans have window of -14 days and may be performed earlier than pre-specified as clinically indicated.

